Depression is a common psychiatric comorbidity with a lifetime prevalence of 16.6% in the United States [25]. Adults with DS have a four- to five-times increased risk of developing depression compared to the general population [13], suggesting that up to 70% of individuals with DS may experience depression in their lifetime. Compared to other known comorbidities associated with DS such as obstructive sleep apnea, congenital heart defects, blood cancers, and cataracts, depression is both relatively more highly prevalent and understudied. No reports on the use of modern antidepressants in DS have been published in the past more than 25 years. Our knowledge of the safety and efficacy of antidepressants in the general population may not be applicable to patients with DS because of the associated medical comorbidities and neurocognitive differences.

The central hypothesis of this project is that adults with major depression and DS will experience an improvement in depressive symptoms after a course of fluoxetine treatment. We also expect that fluoxetine will be safe and well tolerated. This study will provide much needed preliminary prospective

data regarding the effectiveness and tolerability of fluoxetine for these symptoms in DS and is a necessary first step prior to conducting a larger, more definitive placebo-controlled trial.

2. Specific Aims and Objectives

Specific Aim 1: Determine whether a 16-week prospective, open-label trial of fluoxetine shows preliminary evidence of effectiveness, safety, and tolerability in adults with DS and major depressive disorder (MDD).

This aim addresses our central hypothesis that fluoxetine will be effective and safe in the treatment of depression in adults with DS.

- A)** For preliminary evidence of effectiveness, we will require an observed response rate (where response is defined as a 16-week CGI-I rating of “much improved” or “very much improved”) of 35% or greater. We will use the CGI-I rather than a depression scale for our effectiveness criterion because of the absence of existing data supporting the usefulness of common scales for quantifying depression severity in adults with DS.
- B)** For preliminary evidence of safety, we will require no observation of serious or severe adverse effects possibly, probably, or definitely associated with fluoxetine.
- C)** For preliminary evidence of tolerability, we will require an observed drop-out rate due to adverse effects less than 36%.

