A meta-analysis investigating the effectiveness of fluoxetine treatment estimated the intent-to-treat probability of response to treatment as measured using the CGI-I to be 44% [32]. In addition, the lower bound of the 95% confidence interval for response to treatment from our retrospective study excluded values less than or equal to 50%. A sample size of 20 provides a greater than 90% chance of observing a response rate of 35% or greater if the population probability of response is 44% or greater and a greater than 90% chance of observing a response rate less than 35% if the true probability of response is 20% or less. For safety outcomes, if there is a serious or severe adverse event associated with fluoxetine treatment in the population of adults with DS that occurs with a frequency of 10% or greater, we will have an 85% or greater chance of observing it in the study and concluding there are safety concerns with fluoxetine use for depression in adults with DS, assuming at least 90% (n=18) of participants remain in the study long enough to experience the event. For tolerability, assuming at least 85% of patients complete treatment or withdraw due to adverse effects, a sample size of 20 provides greater than 90% chance of observing a dropout rate due to side effects less than 36%, assuming at least 80% of adults with DS and depression in the population can tolerate a 16 week treatment course, and at least an 80% chance of observing a dropout rate due to side effects of 36% or greater assuming no more than 50% of adults with DS can tolerate a 16 week treatment course. Assuming an overall completion rate of 70%, a sample size of 20 also allows estimation of mean changes in depression scale score and mean dosage at study completion with a 95% confidence interval half width of 0.6 standard deviations, assuming a correlation of 0.5 between baseline and week 16 measurements.

Statistical Analysis Plan:

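### With 20 participants and a true response of 44%, the chance of meeting the 35% response criterion is 85%, not the stated greater than 90%

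*Combined protocol and SAP*

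**What the plan says.** Section 2, Aim 1A sets the effectiveness criterion. It begins "For preliminary evidence of effectiveness, we will require an observed response rate" and puts the bar at 35% or more, with a responder being a participant rated 1 or 2 on the CGI-I at 16 weeks. Section 9 (Sample Size Considerations) then gives two probabilities for that rule with 20 participants. The first reads "A sample size of 20 provides a greater than 90% chance of observing a response rate of 35% or greater if the population probability" is at least 44%. The second is a "greater than 90% chance of observing a response rate less than 35% if the true probability of response is 20% or less".

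The 44% comes from a meta-analysis of fluoxetine that, in the plan's words, "estimated the intent-to-treat probability of response to treatment as measured using the CGI-I to be 44" percent. The same paragraph adds that the 95% confidence interval from the group's own retrospective study lay above 50%. The Statistical Analysis Plan in Section 9 counts a missing 16-week CGI-I as non-response, so all participants stay in the denominator. Section 4 gives the number to be included as 25, whereas the sample size paragraph uses 20.

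**The concern.** The two probabilities belong to the same cut-off and can be checked directly from the binomial distribution. At 20 participants, 44% corresponds to 8.8 expected responders, and the criterion is 7. That margin is less than one standard deviation of the count: √(20 × 0.44 × 0.56) = 2.22, against a margin of 1.8. A chance above 90% of clearing the bar therefore looks too high.

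This sentence is the plan's only statement of how likely an effective treatment is to meet the primary criterion. A reader takes from it that both kinds of wrong conclusion have a risk under 10%. If the first figure is wrong, the risk of missing the criterion at the planning value is understated. Section 1 describes the trial as a first step before a larger placebo-controlled trial, so that risk matters for what follows.

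**Working it through.** **Inputs**

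- Number of participants: n = 20 (Section 9, Sample Size Considerations).
- Criterion: observed response of 35% or more (Section 2, Aim 1A). 0.35 × 20 = 7 exactly, so the rule is X ≥ 7.
- Planning response: p = 0.44 or more. The chance is lowest at exactly 0.44, so the claim must hold there.
- Ineffective response: p = 0.20 or less.
- Dropout: the 44% is described as an intent-to-treat figure and missing ratings count as non-response, so no further adjustment is made.

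**Formula.** X ~ Binomial(n, p), P(X ≥ r) = 1 − Σ C(n, k) p^k (1 − p)^(n−k), with k running from 0 to r − 1.

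**Step 1: does the plan use this method?** The paired claim reproduces: P(X ≤ 6 | 20, 0.20) = 0.913, stated as above 90%. So do the other probabilities in the paragraph:

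- Safety, 18 participants: 1 − 0.9^18 = 0.850, stated as 85%.
- Tolerability, 0.85 × 20 = 17 participants. A dropout rate below 36% means at most 6 of 17, since 6/17 = 35.3%. P(X ≤ 6 | 17, 0.20) = 0.962, stated as above 90%. P(X ≥ 7 | 17, 0.50) = 0.834, stated as at least 80%.

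**Step 2: the figure at 44%.** The terms of Binomial(20, 0.44) are:

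| k | 0 | 1 | 2 | 3 | 4 | 5 | 6 |
|---|---|---|---|---|---|---|---|
| P(X = k) | 0.00001 | 0.00014 | 0.00108 | 0.00509 | 0.01699 | 0.04271 | 0.08389 |

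Their sum is P(X ≤ 6) = 0.1499, so P(X ≥ 7) = 1 − 0.1499 = **0.850**. The stated figure is above 0.90. A normal approximation does not recover it either: 0.791 without and 0.850 with a continuity correction.

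**Step 3: could another reading give the stated figure?**

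| Reading | Chance of meeting the rule at p = 0.44 | Chance of not meeting it at p = 0.20 |
|---|---|---|
| n = 20, X ≥ 6 (30%) | 0.934 | 0.804 |
| n = 20, X ≥ 7 (35%) | 0.850 | 0.913 |
| n = 20, X ≥ 8 (40%) | 0.718 | 0.968 |
| n = 25, X ≥ 9 (36%) | 0.843 | 0.953 |

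At n = 25, 0.35 × 25 = 8.75, so 9 responders are needed. No row has both probabilities above 0.90. A cut-off of 6 would give the first property, but 6/20 is 30%, which does not meet the criterion, and it loses the second property. An off-by-one could explain the stated figure, although the documents do not show this.

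Applying dropout only lowers the result. If n falls to 18, 17 or 14, the chance is 0.748, 0.833 or 0.813. If the 44% is multiplied by 0.9, 0.85 or 0.7, it is 0.738, 0.668 or 0.423.

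**Step 4: when is the statement true?** Solving P(X ≥ 7 | 20, p) = 0.90 gives p = 0.467.

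| True response | 0.44 | 0.45 | 0.46 | 0.47 | 0.50 |
|---|---|---|---|---|---|
| P(X ≥ 7), n = 20 | 0.850 | 0.870 | 0.888 | 0.904 | 0.942 |

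With p held at 0.44, the smallest n at which the 35% rule reaches 90% is 40 (X ≥ 14, 0.905).

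**The case against.** The arithmetic is not in dispute; the question is how much it matters. Four points can be made for the plan.

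1. The 15% applies only at exactly 44%. The stated probability fails only between 44% and about 46.7%, and at 50% it is met comfortably (0.942).
2. The plan has a second planning input. Section 6 reports an 82% response among 11 patients. Taking that as 9 of 11, Wilson's method gives a lower limit of 52.3%, which agrees with the plan's statement that values of 50% or less were excluded. If that evidence carries over, the trial does better than 90%.
3. There is no hypothesis test. The 35% is a benchmark in a small open-label study, and the response rate will be reported with a confidence interval. A result of 6/20 would still be seen as 30% with its interval.
4. The shortfall is about 5 percentage points, and the protection against an ineffective treatment is correctly stated.

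The first, third and fourth points stand as limits on the consequence. They do not make the sentence true. The second does not either: the plan attaches the probability to 44%, not to 50%. The pilot was also a retrospective chart review of 11 patients on several SSRIs.

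**Conclusion.** The stated probability is wrong. Under the plan's own rule and planning value, the chance of meeting the criterion is 85.0%, at least 5 percentage points below what is claimed. The chance of missing it is 15.0%, about 1.5 times the implied maximum of 10%. The balance between the two errors is also misdescribed. Both are presented as under 10%, but the risk of missing the criterion at 44% (15.0%) exceeds the risk of meeting it at 20% (1 − 0.913 = 8.7%).

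The result assumes independent participants with a common response probability, the framework in which the other probabilities in the same paragraph reproduce. It also takes 44% as the probability after missing ratings are counted as non-response. It holds at 25 participants as well as at 20. The error lies in one operating characteristic of the primary criterion; the criterion, the endpoint and the planned analysis are unaffected.

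**What to change.** Correct the sentence in Section 9 (Sample Size Considerations) in one of two ways:

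- State that, with 20 participants and a rule of at least 7 responders, the chance of meeting the criterion is about 85% at a true response of 44%, and the chance of not meeting it is about 91% at 20%.
- Keep the greater-than-90% figure and attach it to a true response of about 47% or more, leaving the 20% statement as it is.

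The first is preferable because it keeps the meta-analysis figure as the planning value. If the paragraph is later aligned with the 25 participants in Section 4, the matching figures are 84% and 95% under a rule of at least 9 responders.

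The cost is one protocol sentence and a slightly less favourable figure. No extra participants are needed, and the 35% threshold can stay.

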Specific Aim 2: Collect preliminary data comparing the usefulness of existing depression rating scales in characterizing participants and assessing depression treatment effects.

A variety of outcome measures of depression will be used to better assess their applicability and feasibility in the DS population. The relative performance of the scales will be evaluated based on their sensitivity to change and their association with clinical improvement ratings. Percent of item-level missing data, and any feedback on the appropriateness or ease of use of the scales from participants, including their legal guardians, or study personnel, will also be taken into account.

Specific Aim 3: Estimate the mean therapeutic dose of fluoxetine for adults with DS for treating major depressive disorder (MDD).

We will report the average dose of fluoxetine at the end of 16 weeks of treatment.

We expect our results to: 1) provide preliminary evidence on the safety, effectiveness, and tolerability of fluoxetine for the treatment of MDD in DS; 2) assess the relative performance of existing depression rating scales in DS; and 3) provide information on fluoxetine dosing. Currently there is no prospective evidence on the safety, efficacy, and tolerability of any medication for the treatment of depression in DS. The lack of evidence-based guidelines for the treatment of depression in DS likely contributes to the decreased awareness of and under/misdiagnosis of this largely treatable condition. Adults with DS and comorbid depression may be mistakenly diagnosed with dementia, another neuropsychiatric condition for which there is much greater awareness in DS, but few effective treatments.

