Study staff will provide participants with information on how to access the video conferencing platform. Study staff will launch the video conferencing in a private and secure area and ask participants to refrain from taking screenshots, photographs, or recordings of any kind with any electronic equipment. Study staff will remind participants that video/phone meetings are similar to a home visit and that we may learn more about their home and/or the people living with them than during a visit at the hospital. For example, study staff may learn information that must be reported to public health or public safety authorities. The Informed consent describes the legal obligation to report known or suspected child or elder abuse. If study staff make such a report, the public health and safety authorities can use the information as they see fit and may end up sharing it with other government agencies.

4. Subject Selection

Twenty-five adults (18-45 years of age), with a diagnosis of DS exhibiting clinically significant symptoms of MDD on standardized rating scales will be included in this trial. Subjects will be selected to participate in the study based on the following Eligibility Criteria:

Inclusion Criteria

1. **Age 18-45 years.**
2. **Diagnosis of DS** confirmed via genetic testing or a clinical diagnosis made by a clinician with significant experience treating patients with DS.
3. **Diagnosis of major depressive disorder** based on Diagnostic and Statistical Manual of Mental Disorders, Fifth Edition (DSM-5) criteria, confirmed through the Structured Clinical Interview for DSM-5 (SCID-5).
4. **Moderately severe depression as evidenced by a Montgomery-Asberg Depression Rating Scale (MADRS) score of 20 or greater** at Screen and Baseline. A severity score on the MADRS was chosen as an inclusion criterion since it has been demonstrated to be sensitive to change in adults with MDD [27].
5. **A Clinical Global Impression Severity Item score ≥ 4 (moderate)** for depression symptoms at Screen and Baseline.

Exclusion Criteria

1. **Active primary diagnosis of obsessive-compulsive disorder, posttraumatic stress disorder, bipolar disorder, psychosis, or substance use disorder.** These disorders are exclusionary since the primary treatment of these disorders may require acute psychosocial or medication treatments that would confound the assessments used in this study. We will evaluate for these disorders using the corresponding SCID-5 modules.

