6. STUDY PROCEDURES

Screen Visit:

The purpose of the *screen visit* is to ensure participants meet the eligibility criteria as defined above in Subject Selection.

In order to distinguish subjects who should be excluded due to profound intellectual disability from subjects who are not able to provide assent, the presence of severe or profound intellectual disability will be determined based on a clinical evaluation by a board-certified psychiatrist and psychologist (both experienced in the care of and conducting research involving adults with developmental disabilities) which takes into account a clinical assessment, review of cognitive testing (if available), and the clinically appropriate use of standardized scales (Stanford-Binet Intelligence Scales Weschler Abbreviated Scale of Intelligence, Second Edition; or Developmental Profile, Fourth Edition).

If it is clear that participants meet all eligibility criteria, the *Screen* and *Baseline* visits may be combined into a single visit during which the Montgomery-Asberg Depression Rating Scale (MADRS) would only be conducted once.

Baseline Characterization:

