All subjects will have a baseline psychiatric diagnostic evaluation done to gather a thorough developmental, medical, and psychiatric history, as well as a mental status examination, and vital signs will be obtained for subjects evaluated in the clinic if subject cooperation allows. This will be determined by a board-certified psychiatrist experienced in the care of adults with developmental disabilities. Examples of lack of cooperation due to emotional dysregulation include refusal to participate, repeated requests for a break, and verbalizations of distress. Lack of cooperation may occur and is expected occasionally in this population. In visits where subject measures cannot be completed, measures from the caregiver will be collected only. In clinical care it is standard for caregivers to be the primary reporters of response to medication, therefore it is still valuable to collect non-primary outcome measures from the caregiver. Lack of cooperation would only become withdrawal of assent if behaviors stated in the assent section occur, for example regularly refusing to take the medication. If the visits are conducted remotely, not all vital signs will be obtained. The medical history will be aimed at ruling out other medical conditions that could exacerbate depression or behavioral symptoms (e.g., chronic gastrointestinal disease, obstructive sleep apnea, thyroid disease). The following standardized scales and testing may also be conducted. If cognitive testing has been completed within the past five years, these medical records may be requested and reviewed to inform study eligibility criteria.

- 1. Stanford-Binet Intelligence Scales, Fifth Edition (SB-5)** [33]. The SB-5 may be used to calculate an abbreviated battery IQ. The abbreviated IQ was chosen to limit subject burden given that a number of other measures will be conducted at screening.
- 2. The Wechsler Abbreviated Scale of Intelligence, Second Edition (WASI-II)** [34]. The WASI-II can also be administered remotely and will be used for subjects depending on age and ability.
- 3. Developmental Profile, Fourth Edition (DP-4)** [35]. If patients are unable to obtain a valid score on the SB-5 ABIQ or WASI-II due to constraints of a virtual visit or significantly delayed cognitive skills, the Cognitive and Adaptive Behavior subscales of the Developmental Profile (DP-4) Parent/Caregiver Interview Form may be administered. DP-4 scores will require a minimum age-equivalency cutoff of 24 months.

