We will estimate percentage response to fluoxetine treatment, and corresponding 95% confidence interval, for adults with DS using the proportion of participants with CGI-I scores ≤ 2 at 16 weeks. Participants with missing 16-week CGI-I scores will be treated as non-responders. Frequency of all side effects and adverse events and corresponding 95% confidence intervals will be tabulated. Percent tolerating treatment and corresponding 95% confidence intervals will be estimated using the proportion of participants who did not withdraw from the study before 16 weeks due to reasons other than side effects or an adverse event who discontinue treatment due to side effects or an adverse event. We will also use the 16-week study retention rate and corresponding 95% confidence interval, calculated as the proportion of the participants enrolling in the study who remain in the study for 16 weeks, as a measure of feasibility.

To estimate changes in depression scale scores, including the MADRS, HAM-D, GDS-LD, and GDS-CS, we will use repeated measures linear regression models, as implemented in PROC MIXED in SAS and fit using REML estimation, with repeated measurements of clinical scores as outcomes and time, in categories, as the predictor. We will allow unstructured covariance between repeated measurements from the same participant. Our primary interest will be only in the difference between baseline and week 16 scores, but all observed scores will be included as outcomes, given that partially observed scores may be informative for estimation. We will obtain an estimate of 16-week change and corresponding 95% confidence interval using a contrast of the week 16 and baseline model parameters. Sensitivity to change will be compared between scales using standardized effect sizes, calculated using the model-estimated 16-week change in each outcome divided by 1) the model-estimated standard deviation of the outcome at baseline and 2) the model-estimated standard deviation of the change score. Spearman correlations will quantify the strength of association between change in depression scale score and CGI-I ratings among those with observed 16-week data. We will also tabulate and compare the percent of item-level missing data for each scale.

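### Aim 2 compares four depression scales on effect-size point estimates with no interval, and the MADRS entry cut-off can tilt that comparison towards MADRS

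*Combined protocol and SAP*

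**What the plan says.** Specific Aim 2 (Section 2) sets the criteria: "The relative performance of the scales will be evaluated based on their sensitivity to change and their association with clinical improvement ratings". Item-level missing data and user feedback also count.

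Section 9, Statistical Analysis Plan, fits a repeated-measures model to each of MADRS, HAM-D, GDS-LD and GDS-CS. It then states: "Sensitivity to change will be compared between scales using standardized effect sizes, calculated using the model-estimated 16-week change in each outcome divided by 1", where the closing 1 numbers the first divisor, the baseline SD, and the second divisor is the SD of the change score. A 95% interval is planned for each scale's 16-week change, but none for an effect size or for a difference between scales. Neither index is given priority.

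Section 4 requires "Moderately severe depression as evidenced by a Montgomery-Asberg Depression Rating Scale (MADRS) score of 20 or greater" at Screen and Baseline. The other three scales have no cut-off. CGI-S of at least 4 and a SCID-5-confirmed diagnosis also gate entry, but neither is among the scales compared. Section 6 lets Screen and Baseline be one visit, in which case "the Montgomery-Asberg Depression Rating Scale (MADRS) would only be conducted once".

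On who is measured, Section 6 makes HAM-D optional and adds: "In visits where subject measures cannot be completed, measures from the caregiver will be collected only". In Table 1, GDS-LD appears only as a subject assessment, given when the participant's abilities allow.

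**The concern.** Selecting on a score does two things to that score. It narrows the baseline spread, which is the divisor of the first index. It also makes later scores fall back towards the mean, which adds to the numerator of both indices. The other three scales feel this only through their correlation with MADRS. Part of a MADRS lead, mainly on the baseline-SD index, could therefore come from the entry rule. The plan does not mention this.

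Two further features make the comparison hard to read. With about 14 completers the differences between scales are very noisy, and without an interval a reader cannot see that. If HAM-D or GDS-LD is missing for some participants, effect sizes from different people are being compared.

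At stake is one criterion of Aim 2. Section 2 hopes the results will guide which scale non-specialists use.

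**Working it through.** **Inputs from the documents (Section 9, Sample Size Considerations).** 70% of 20 gives 14 completers, "assuming a correlation of 0.5 between baseline and week 16 measurements".

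**Inputs assumed.** Cross-scale correlation r, true change of 1 pre-gate SD on every scale, and the position of the cut-off in the candidate population.

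**The plan's own figure.** SD(change) = SD × √(2(1 − 0.5)) = 1.00 SD. Half-width = t(0.975, 13)/√14 = 2.160/3.742 = 0.577 SD. The stated 0.6 reproduces. At this correlation the two indices coincide when there is no gate.

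**Effect of a gate, algebra.** Let MADRS at baseline be standard normal and kept above c. Write λ for the mean after truncation and δ for the variance lost. With ρ = 0.5:
- mean change = 1 + (1 − ρ)λ
- baseline SD = √(1 − δ)
- change SD = √(2(1 − ρ) − (1 − ρ)²δ)

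For an ungated scale, replace λ by rλ and δ by r²δ. If the gate excludes 30%, λ = 0.497 and δ = 0.507. Taking r = 0.6:
- MADRS: change 1.25, baseline SD 0.70, change SD 0.93; effect sizes 1.78 and 1.34.
- Ungated scale: change 1.15, baseline SD 0.90, change SD 0.98; effect sizes 1.27 and 1.18.
- Ratio MADRS/ungated (1.00 is fair): 1.40 on baseline SD, 1.14 on change SD.

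If the gate excludes 5%, the ratios are 1.10 and 1.04. Over 135 settings (5-50% excluded, ρ 0.3-0.7, r 0.4-0.8, change 0.5-1.5 SD) they run from 1.05 to 2.30 and from 1.01 to 1.63. The change-SD ratio was the smaller in every setting and never below 1.

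**Effect at n = 14, simulation.** Four equally responsive scales, r = 0.7, screen-baseline correlation 0.8 (assumed), and a CGI-S gate at the same cut-off as MADRS. Ranking first is a summary used here, not a rule in the plan; chance is 25%.

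| Cut-off (pre-gate SD) | Pass CGI-S, fail MADRS | MADRS first, baseline SD | MADRS first, change SD |
|---|---|---|---|
| −1.5 | 4-6% | 33-34% | 28-29% |
| −1 | 9-12% | 41-44% | 31% |
| 0 | 25-31% | 66-68% | 38-39% |

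With CGI-S cut at the mean and MADRS at −1.5, the shares are 26-27% and 25-26%, so the tilt nearly vanishes. For cut-offs from −1 to 0, the bias in MADRS minus another scale is about 0.2 to 0.6 on baseline SD, against a sampling SD of about 0.45 to 0.7. On change SD it is 0.06 to 0.14, against about 0.4.

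**Is change SD a safe sole basis?** Suppose true change varies between people with SD 0.8 (assumed) around a mean of 1, with the reference scale's baseline-week 16 correlation held at 0.5 and no gate.
- Reference change variance = 1 + 1.64 − 2 × 0.5 × √1.64 = 1.36, of which 0.64 is true variation and 0.72 is not.
- A scale 50% more responsive has change variance 0.72 + 1.5² × 0.64 = 2.16.
- Change-SD effect sizes: 1.5/√2.16 = 1.02 against 1/√1.36 = 0.86, a ratio of 1.19. On baseline SD the ratio is the full 1.50.

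With the gates on and HAM-D truly 50% more responsive, HAM-D ranks first in 51-80% of trials on baseline SD and 38-54% on change SD. If true change is identical in everyone, the order reverses for cut-offs −1 to 0: 48-71% against 71-79%. With an SD of 0.5 the result is mixed.

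The change-SD index also depends on each scale's own baseline-week 16 correlation. With no gate and equal mean change, a MADRS correlation of 0.6 against 0.5 elsewhere gives a MADRS effect size of 1/√0.8 = 1.12 against 1.00. MADRS then ranks first in 35% of trials on change SD and 24% on baseline SD.

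**Interval width.** For a paired bootstrap on complete pairs, the median 95% half-width with 14 pairs is 0.96-1.41 (baseline SD) and 0.78-0.93 (change SD). With 10 pairs it is 1.32-1.95 and 1.07-1.27. With equal scales and 14 pairs, the interval lies wholly on the MADRS side in 8-22% and 6-9% of trials, against a nominal 2.5%.

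**The case against.** The best defence is that CGI-S and SCID-5 may already do the selecting, leaving the MADRS cut-off little to exclude. That stands as a possibility: the tilt can be near zero, and the documents give no screening figure to settle it.

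It is also true that the plan picks no winner, reports both indices, and weighs CGI-I association, missing data and feedback as well. At this sample size the tilt is smaller than one trial's sampling noise. But noise has no direction and an interval would display it, whereas this tilt has a known direction and more participants would not remove it. The plan as written shows the reader neither.

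A reader might infer that the change-SD index should become the sole basis because it is tilted less. The documents do not support that. The gain depends on everyone having much the same true change, yet Section 9 plans around a 44% response rate, which suggests mixed response. When response varies, that index penalises the more responsive scale. Planning both indices is sound.

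Restricting the analysis to complete pairs alone would also discard partial data that Section 9 deliberately keeps. The paired comparison therefore belongs beside the model-based one, not in its place.

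**Conclusion.** The point holds as a minor one. The between-scale comparison rests on bare point estimates, one of which can be inflated by the entry rule and some of which may come from different participants. Among equal scales, MADRS would rank first in 33-68% of trials on baseline SD and 28-39% on change SD, or about 26% on both if CGI-S does most of the selecting. These figures assume normal scores, r = 0.7, 14 completers and equal true change. The documents give neither the cross-scale correlation nor the share the gate excludes.

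Two further readings go too far. One is that any MADRS lead would be an artefact: the size is unknown and may be near zero. The other is that the main result is compromised: the primary outcome is CGI-I response, which uses neither index. The documents also do not say how often HAM-D or GDS-LD will be missing, so the different-participants problem is a possibility, not a forecast.

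**What to change.** In Section 9, Statistical Analysis Plan:

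1. Keep both planned indices and do not name change SD as the sole basis.
2. Add a 95% interval for each between-scale difference in effect size, by resampling participants and refitting the planned models so that all observed scores are kept. Show beside it the comparison restricted to participants with both scales observed at baseline and week 16.
3. State that selection on MADRS of 20 or more can inflate the MADRS effect size, mainly on baseline SD and to a smaller degree on change SD. Add that a MADRS lead seen only on baseline SD will not be taken as greater sensitivity. Report the share of candidates with CGI-S of at least 4 who fail the MADRS cut-off.

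Cost: some wording, a bootstrap and one screening count, with no new visits or measures. The intervals will be wide at about 14 completers, and wider for pairs involving a scale that is often missing. They do not remove the residual MADRS bias, which is why the caveat is needed as well. Each unstructured model over five visits has 5 × 6/2 = 15 covariance parameters, so some refits may fail to converge; the number that fail should be reported.
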